Further tumor imaging will be performed in all patients every 9 weeks for the first 46 weeks and then 12-weekly thereafter until progression (which may be confirmed). On each occasion, tumor assessments will include imaging of the chest, abdomen and pelvis. Additional anatomy, including brain and bone, should be imaged based on signs and symptoms of individual patients. Disease response will be evaluated at these time points according to RECIST 1.1. If either or both of the study treatments are stopped for any reason other than confirmed progression, tumor imaging will continue every 12 weeks until confirmed progression.

Patients who are suspected of having a complete or partial response will have their response confirmed at the next scheduled assessment or no earlier than 4 weeks (28 days) later.

Blood sampling for PBMC and Axl signaling and inhibition biomarker analysis will be performed at Screening, Cycle 1, Days 4 and 8 and every study visit thereafter until Cycle 9, Day 1.

Blood sampling for BGB324 pharmacokinetic (PK) analysis will be performed on blood samples taken on:

- Cycle 1, Days 1 and 3 as follows: pre-dose and at 2, 4, 6 and 8 hours post dose;
- Cycle 1, pre-dose on Days 2, 4, 8 and 15;
- Cycles 2 and 3, pre-dose (study days 22 and 43 respectively).

Blood sampling for future pembrolizumab PK analysis will be performed on blood samples taken pre-dose on Cycle 1, Days 1 to 4, 8 and 15 and then pre-dose at Cycles 2 and 3 (study days

22 and 43 respectively). These samples will be frozen and stored centrally for future reference and analysis.

Patients with tumor amenable to repeat sampling may have additional fresh biopsies taken on up to 2 occasions post-dose at time points agreed between the Investigator and the patient. Where possible, efforts will be made to obtain follow up biopsy material where a patient has responded to treatment or has progressed on treatment.

Further details on sample collection and handling for all PK and biomarker assessments are described in the Laboratory Manual.

Patients who discontinue BGB324 treatment (for reasons other than disease progression) may be able to continue with (monotherapy) pembrolizumab until 106 weeks (that is, 35 completed cycles of pembrolizumab). These patients will no longer be required to have the following assessments from 6 weeks after the discontinuation of BGB324 (unless clinically indicated):

- ECG;
- Echocardiogram (or Multi Gated Acquisition Scan (MUGA));

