- Optional tumor biopsy (for example at subsequent progression);
- Biomarker sampling.

The Post Treatment Visit will occur 30 days after the patient has discontinued both treatments on study. Patients who withdraw from either or both study treatments prior to disease progression will continue to have tumor imaging assessments every 12 weeks until disease progression is documented (and confirmed, if necessary). The date of disease progression will be captured.

Subsequent to disease progression (confirmed if necessary), patients will continue to have their survival status checked every 12 weeks until death or the Last Patient Last Visit (LPLV) date (see [Section 8.6](#)), whichever is earlier. Survival status can be checked via telephone.

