**Footnotes:**

- 1 A pregnancy test is required within 3 days prior to C1D1. A negative pregnancy test may be confirmed by urine or blood test. Where a urine test is positive or equivocal, a blood test must be performed to confirm the result. Patients requiring confirmation of post-menopausal status will have FSH and oestradiol levels assessed at Screening. Where applicable, and in accordance with local regulations, a pregnancy test should be conducted at each cycle (or monthly).
- 2 Vital signs will include temperature, systolic blood pressure, diastolic blood pressure, heart rate and respiratory rate. On pembrolizumab dosing days, vital signs will be taken both pre-dose and at the end of infusion.
- 3 Physical examination includes height at Screening and weight at Screening and the start of each cycle. After Screening, further assessments may be symptom-directed.
- 4 Coagulation parameters may be assessed from the Hematology sample.
- 5 Thyroid function testing may be assessed from the Clinical chemistry sample.
- 6 For each ECG assessment, triplicate 12-lead ECGs must be taken less than 5 minutes apart, with the patient having rested for at least 10 minutes in the supine position prior to assessment. Time points are relative to BGB324 dosing: C1 D1 pre-dose and 6 hours after dose; D2 pre-dose; D3 pre-dose; D4 pre-dose. All other time-points are pre-dose unless clinically indicated. If a patient permanently discontinues BGB324 (but continues pembrolizumab), the last ECG will be performed at the next pembrolizumab administration. If a patient has BGB324 interrupted for 14 days for toxicity or QTC prolongation, an ECG will be conducted twice weekly for the following 2 weeks once a patient restarts BGB324 daily dosing.
- 7 Tumor imaging will be performed at Screening, then every 9 weeks for the first 46 weeks, and then every 12 weeks thereafter (+/- 7 days). A tumor response or disease progression should be confirmed no less than 28 days after the initial finding. If treatment administration is misaligned with weeks (e.g. because of treatment delay), the tumor imaging schedule should be maintained by week number and continue if necessary. The schedule of disease assessments is every 12 weeks once a patient has stopped (one or both study treatments) or completed their treatment in the absence of progression. These may continue into Follow Up.

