- c) All sample times are approximate and every effort must be made to take PK samples at specified times. Actual sampling times must be recorded in order to assess result relative to BGB324 or pembrolizumab dose. Please refer to the local Laboratory Manual for full details on PK sample collection, time-points, processing, storage and shipment.
- 13 D1 of next cycle would be "D22" of the previous cycle.
- 14 A Post Treatment Visit is to be conducted up to 30 days (+/-3 days) from last dose of study drugs. Adverse events and concomitant medications must be assessed to 30 days. Some AEs must be assessed for longer (see [Section 7.4.3](#) and [Section 7.5](#)). Other assessments may be carried out between 7-30 days from last dose. Tumor imaging and disease assessment is only required where is part of next scheduled assessment (where patient has not yet progressed) or to confirm response or progression.
- 15 Tumor imaging and disease assessment will continue every 12 weeks from the last dose of study drug where the patient has not yet progressed or to confirm response or progression. An assessment of disease status, survival status and details of any anti-cancer therapies received after last dose of study drug will also be collected. Survival status (every 12 weeks) can be collected by telephone.
- 16 Echocardiogram (or MUGA) will be conducted every 6 months whilst a patient receives BGB324. If a patient discontinues BGB324 (but continues pembrolizumab), a final echocardiogram (or MUGA) will be conducted only if one is scheduled in the following 6 weeks.
- 17 Demography – race, ethnicity, gender, age (birth month and year).
- 18 Hematology and Clinical Chemistry to be assessed at a suitable time prior to administration of study treatment(s).

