## 5 STUDY SCHEDULE

The study consists of a Screening period, Treatment period, Post Treatment Visit and Follow-up period. Patients will attend the clinic for Screening period assessments up to 28 days before receiving the first dose of study treatment. The Post Treatment Visit will occur 30 days after the patient has discontinued both study treatments. All patients will continue in follow-up visits and continue to have their disease assessed and scanned (unless progression of disease has already been confirmed) and for survival status.

The study schedule will continue in keeping with the Study Assessment calendar. Patients will be required to visit the study sites for each study visit (which includes each pembrolizumab dose). From Cycle 2 onwards, a tolerance window of +/- 3 days is permitted. Pembrolizumab that cannot be given within these tolerance windows will be treated as a missed dose, although it is acceptable to have a pembrolizumab dose interruption for up to 3 weeks (for reasons other than toxicity). See [Section 6.6.3](#) for full details on pembrolizumab dose interruptions, including the duration of interruption for toxicity.

It is important that the calendar schedule for tumor assessment relative to Cycle 1, Day 1 is maintained (subject to permitted tolerance windows). If treatment administration is misaligned with weeks (e.g. because of treatment delay), the tumor assessment schedule should be maintained by week number ([Table 3](#), [Table 4](#) and [Table 5](#)). The schedule of disease assessment is every 12 weeks once a patient has stopped one or both or completed their (combination) treatment in the absence of progression.

Assessments requiring specific timing relative to the BGB324 or pembrolizumab dose are described in the footnotes to Schedule of Study Assessment [Table 4](#) and [Table 5](#).

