- ~ Physical examination
- ~ Clinical chemistry
- ~ Hematology
- ~ Coagulation
- ~ Urinalysis

- ~ ECG (triplicate test; pre-dose)
- ~ BGB324 oral dosing 200 mg (consecutive daily dosing 21 day cycle)
- ~ PK sampling BGB324 (pre-dose)
- ~ PK sampling for storage (pre-dose) - pembrolizumab
- ~ Adverse events
- ~ Concomitant medication

Cycle 2-35 (every 3 weeks), Day 1

- ~ ECOG PS
- ~ Vital signs
- ~ Physical examination
- ~ Clinical chemistry
- ~ Hematology
- ~ Coagulation
- ~ Urinalysis (performed on Cycle 2 Day 1 only)
- ~ Pregnancy test (if applicable)
- ~ Thyroid function tests (performed at Cycles 3, 5, 7, 9, 11, 13, 15, 17 only in Year 1 and then Cycles 19, 21, 23, 25, 27, 29, 31, 33, 35 in Year 2)
- ~ Echocardiogram (or MUGA) (performed at Cycles 9 and 17 in Year 1 and then Cycles 25 and 33 in Year 2)
- ~ ECG (triplicate test; pre-dose)
- ~ Tumor imaging (performed at Cycles 4, 7, 10, 13, 16, 20, 24, 28, 32 or Weeks 10, 19, 28, 37, 46, 58, 70, 82, 94, 106, and then every 12 weeks until progression)
- ~ Disease assessment (performed at Cycles 4, 7, 10, 13, 16, 20, 24, 28, 32 or Weeks 10, 19, 28, 37, 46, 58, 70, 82, 94, 106, and then every 12 weeks until progression)
- ~ Tumor biopsy (up to 2 optional post treatment biopsies)
- ~ Biomarkers (performed only at Cycles 2-9)
- ~ Pembrolizumab 200 mg fixed dose (infusion)
- ~ BGB324 dosing 200 mg (daily oral dosing 21 day cycle)
- ~ PK sampling BGB324 (pre-dose Cycles 2 and 3 only)
- ~ PK sampling - pembrolizumab (pre-dose Cycles 2 and 3 only)
- ~ Adverse events
- ~ Concomitant medication

Post Treatment Visit (only after both treatments are discontinued in either Year 1 or Year 2)  
+30 days from last dose of study treatment(s)

- ~ ECOG PS
- ~ Vital signs
- ~ Physical examination
- ~ Clinical chemistry
- ~ Hematology
- ~ Coagulation

- ~ Urinalysis
- ~ Thyroid function tests
- ~ ECG (triplicate test)
- ~ Adverse events
- ~ Concomitant medication
- ~ Tumor imaging (where applicable – for example, to confirm progression)
- ~ Disease assessment (where applicable – for example, to confirm progression)
- ~ Tumor biopsy (optional) at progression

Follow-Up (if the patient has had a Post Treatment visit in Year 1 or Year 2) - every 12 weeks

- ~ Concomitant medication (where applicable)
- ~ Tumor imaging (where applicable; every 12 weeks until disease progression)
- ~ Disease assessment (where applicable; every 12 weeks until disease progression)
- ~ Subsequent anti-cancer treatment

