### 5.3.10 Tumor imaging

Efficacy endpoints in this study, including ORR, DoR, PFS will all be based on tumor imaging evaluation by RECIST 1.1.

RECIST assessments will be performed at the times given in Schedule of Study Assessment Table 4 and Table 5 using contrast-enhanced CT (preferred method) or MRI assessments of chest, abdomen, and pelvis. X-ray scans can be used where appropriate. Bone scans and brain scans should be conducted in the 6 weeks prior to study entry. Subsequently, x-ray, bone scans and brain scans will be used as appropriate. Additional anatomy should be imaged based on signs and symptoms of individual patients at baseline and follow-up.

Baseline assessments should be performed no more than 28 days before start of study treatment (6 weeks for brain and bone scans), and ideally should be performed as close as possible to the start of study treatment. The Screening imaging assessments must confirm the patient has measurable disease per RECIST 1.1 (see [Section 3.1](#)).

For each patient, the same modality used at Screening must be used serially throughout the duration of study participation. All imaging procedures will be performed according to standard local imaging protocols to ensure consistency across study assessments.

All radiological and non-radiological (e.g. MRI) scans will be reviewed by the local site investigator; and if possible, stored electronically (de-identified with the patient's notes) at site.

A maximum of 5 target lesions (TLs) must be selected at baseline. All target lesions are measurable. Target lesions should be selected on the basis of their size (longest diameter for non-nodal lesions or short axis for nodal lesions), but in addition should be those that lend themselves to reproducible repeated measurements. All remaining lesions present at baseline are considered non-target, irrespective of whether they are measurable.

Disease assessments will be performed as per the schedule described in [Table 3](#), [Table 4](#) and [Table 5](#) – that is, every 9 weeks  $\pm 7$  days for the first 46 weeks relative to the date of first treatment administration and then every 12 weeks  $\pm 7$  days thereafter until confirmed objective disease progression as defined by RECIST 1.1 (irrespective of a delay to treatment, or the reason for stopping treatment or subsequent therapy).

Any other sites at which new disease is suspected should also be adequately imaged at a follow-up visit.

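### The protocol sets two conflicting tumor-imaging calendars, with different anchors, for patients who stop one or both drugs without progression before Week 46

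*Protocol*

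**What the plan says.** **Fixed calendar.** Section 5.3.10 sets disease assessments every 9 weeks (±7 days) for the first 46 weeks from the date of first treatment, then every 12 weeks until confirmed progression, "irrespective of a delay to treatment, or the reason for stopping treatment or subsequent therapy". Section 8.5 repeats the interval, the anchor and most of that qualifier. It adds that the schedule is meant to limit bias from patients being assessed at unequal frequencies. Section 5.1.1 lists the resulting scan weeks: 10, 19, 28, 37, 46, 58, 70, 82, 94 and 106.

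**12-weekly rule after stopping.** Four places change the interval once a drug is stopped without progression, and none has a Week 46 condition:
- Synopsis, Study Procedures and Assessments, for either or both treatments stopped: "tumor imaging will continue every 12 weeks until confirmed progression".
- The same part of the synopsis, with the Post Treatment Visit: "Patients who withdraw from either or both study treatments prior to disease progression will continue to have tumor imaging assessments every 12 weeks".
- Footnote 7 to Tables 4 and 5: "The schedule of disease assessments is every 12 weeks once a patient has stopped (one or both study treatments".
- Section 5: "The schedule of disease assessment is every 12 weeks once a patient has stopped one or both or completed their (combination) treatment".

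**Anchor.** The same paragraph of Section 5 stresses that the "calendar schedule for tumor assessment relative to Cycle 1, Day 1 is maintained". Footnote 15, for the Follow Up column, says: "Tumor imaging and disease assessment will continue every 12 weeks from the last dose of study drug". The Follow-Up list in Section 5.1.1 has "Tumor imaging (where applicable; every 12 weeks until disease progression", with no starting point. Footnote 7 gives no starting point for a patient who stops only one drug.

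**The concern.** For a progression-free patient who stops a drug before Week 46, the two sets of passages require scans on different dates. A site that follows one set departs from the other.

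The protocol expects such patients. Sections 3.3 and 4.2 let a patient continue on either drug alone, and Section 6.6.1 requires BGB324 to be discontinued if toxicity does not recover within 14 days.

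Section 8.12.2.3 dates PFS at the scan where progression is first seen, and Section 8.12.2.1 ends duration of response at the progression date. If the scan interval lengthens because a patient stopped a drug, recorded progression shifts for a reason unrelated to the disease. Sites that read the protocol differently would also produce data on different grids. An analysis plan cannot recover scans that were never taken.

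For the primary endpoint, Sections 8.2.2 and 8.3 rest on each patient having the potential for at least two scans in 24 weeks. One reading of the anchor removes the second scheduled scan for some patients.

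**Working it through.** **1. Reproduce the protocol's calendar.** Scan weeks are 1 + 9i for i = 1 to 5, then 46 + 12i. This gives 10, 19, 28, 37, 46, 58, 70, 82, 94, 106, exactly as listed in Section 5.1.1.

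**2. Apply each rule to the same patient** (protocol week numbers, scans after the stop):

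| Last dose | Fixed calendar | 12-weekly from last dose | 12-weekly from last scheduled scan |
|---|---|---|---|
| Week 7 | 10, 19, 28, 37, 46 | 19, 31, 43, 55 | 13, 25, 37, 49 |
| Week 16 | 19, 28, 37, 46 | 28, 40, 52 | 22, 34, 46 |
| Week 25 | 28, 37, 46 | 37, 49 | 31, 43, 55 |

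For a last dose in Week 16, the last-dose anchor leaves 28 − 10 = 18 weeks between scans, where 9 are planned. Over ten stopping weeks from Week 4 to Week 40, that gap was 13 to 18 weeks. In each of the ten cases at least one scan fell outside the ±7 day window of the fixed calendar.

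**3. Count scans within 24 weeks of first dose.** From here weeks are elapsed since first dose, so Week 10 is 9 elapsed weeks, and s is the stopping week.
- Fixed calendar: scans at 9 and 18, so 2.
- 12-weekly from the last scheduled scan (or first dose if none): 12 and 24 if s < 9; 9 and 21 if s is 9 to 17; 9 and 18 if s ≥ 18. Always 2.
- 12-weekly from the last dose: for s = 1 to 8, the scan at s + 12 falls inside and s + 24 falls outside, so 1. For s = 9 to 12, scans at 9 and s + 12 ≤ 24, so 2. For s = 13 to 17, the scan at 9 and the next at 25 or later, so 1. For s ≥ 18, 2.

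**4. Count scans through Week 46** (45 elapsed weeks), for stops at weeks 1 to 24. Fixed calendar: 5. 12-weekly rule, either anchor: 3 or 4.

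**5. Delay from progression to the detecting scan.** As a rough guide, the mean delay is half the interval: 9/2 = 4.5 weeks against 12/2 = 6 weeks, a difference of 1.5 weeks. A simulation refines this. It drew 400,000 progressions per combination, exponential after the stop, with medians of 8, 12, 16 and 26 weeks and stops at 3, 6, 9, 12, 18, 24 and 30 weeks, counting scheduled scans only:

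| Rule | Mean delay (weeks) | Added to fixed calendar (weeks) |
|---|---|---|
| Fixed calendar | 4.3–5.5 | – |
| 12-weekly from last scheduled scan | 5.5–7.0 | 0.4–1.9 |
| 12-weekly from last dose | 6.3–7.0 | 0.8–2.7 |

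These are averages, and single dates can move earlier. With a last dose in Week 16 and the last-scan anchor, progression in Week 20 is dated Week 22 instead of Week 28. The overall PFS median can therefore shift either way.

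**6. Design figures.** Exact binomial calculation for 28 then 56 patients gives power 80.5% (Section 8.1 states 80.6%) and one-sided error 0.0483 (stated 0.048). The imaging conflict does not enter these figures.

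**The case against.** The strongest defence is that the text is a general rule with an exception. Footnote 7, Section 5 and the first synopsis passage give the general schedule or its calendar first and the stopping rule afterwards. Section 5.3.10 refers to Tables 3, 4 and 5, so it arguably imports footnote 7. Its qualifier follows the words on continuing until confirmed progression, and could mean only that imaging continues whatever the reason for stopping. The bias sentence in Section 8.5 comes straight after an instruction on unscheduled scans. Footnote 15 concerns patients off both drugs.

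This does not remove the conflict. Sections 5.3.10 and 8.5 both state the interval and the anchor explicitly, and Section 5.3.10 extends its qualifier to treatment delay, which bears on timing and not on how long imaging lasts. Section 8.5 has neither a stopping exception nor a reference to the tables. Even on the exception reading, the starting point of the 12 weeks after a single-drug stop is not stated.

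The points on size largely stand. The trial is single-arm, PFS is secondary and descriptive, and the decision rules use response rate alone. The simulation leaves out deaths, clinically indicated scans and Post Treatment Visit imaging, so it probably overstates the delay. The loss of a second scan within 24 weeks requires the last-dose anchor.

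**Conclusion.** The inconsistency is real and should be fixed before sites rely on the schedule. Two intervals apply to the same patients before Week 46, and the anchor is first dose, last dose or unstated depending on the passage. After Week 46 both rules are 12-weekly and only the anchor can differ.

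The effect is modest: one to two fewer scheduled scans through Week 46 and an average added delay of about 1 to 2 weeks in dating progression, confined to patients who stop a drug early without progression. That delay rests on the exponential model and the ranges of medians and stopping times used. The effect on the trial as a whole cannot be sized because the protocol does not say how many such patients to expect.

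For response rate, the number of scheduled scans within 24 weeks falls from 2 to 1 only if scans run from the last dose and the patient stops at about weeks 1 to 8 or 13 to 17. Even then a Post Treatment Visit scan or an unscheduled confirmatory scan may supply another.

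**What to change.** Adopt one calendar, anchored to Cycle 1, Day 1 and independent of treatment status: Weeks 10, 19, 28, 37 and 46, then every 12 weeks until confirmed progression. This uses the weeks already listed in Section 5.1.1 and serves the equal-frequency aim stated in Section 8.5. Specifically:
- Remove the switch to 12-weekly imaging on stopping from both synopsis passages, footnote 7 and Section 5.
- Remove the last-dose anchor from footnote 15.
- In the Follow-Up list of Section 5.1.1, replace the bare 12-weekly wording for imaging and disease assessment with a reference to Table 3. State that the 12-weekly grid continues beyond Week 106, where that table ends.

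The cost is protocol wording, plus one to two scans per progression-free early stopper (5 against 3 or 4 through Week 46), which Sections 5.3.10 and 8.5 as written already call for.
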